4.6. Intra-subject Monotherapy to Combination Arm Crossover

Subjects on monotherapy (Arm A) will be allowed to cross over (to Arm B) to be treated with the combination at RP2D at the time of progression. The crossover is allowed if a patient has not experienced intolerable toxicity on mono therapy, and has experienced disease progression (including AML) according to 2006 IWG criteria. In each case, approval for crossover has to be granted by GSK Medical Monitor.

The study site is required to provide the safety and disease assessment data of the subject, and the completed crossover form (Refer to Study Procedure Manual) at least 48 hrs prior to the crossover. The medical monitor will review the data and provide the approval for crossover with a signed crossover form.

The crossover to combination treatment Arm B should occur as quickly as possible and no later than within 4 weeks of disease progression. All assessments and samples required at the “crossover visit” as described in the Time and Event table (Section 7.1) must be completed at the time of crossover. The disease assessment and safety laboratory results at the time of crossover will be considered a new baseline as the subject starts combination treatment and continue on with the next visit (from the mono therapy).

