7. STUDY ASSESSMENTS AND PROCEDURES

Protocol waivers or exemptions are not allowed with the exception of immediate safety concerns. Therefore, adherence to the study design requirements, including those specified in the Time and Events Table, are essential and required for study conduct.

This section lists the procedures and parameters of each planned study assessment. The exact timing of each assessment is listed in the Time and Events Table Section [7.1](#)

- The timing and number of planned study assessments, including safety, PK, PD/biomarker assessments may be altered during the course of the study based on newly available data (e.g., to obtain data closer to the time of peak plasma concentrations) to ensure appropriate monitoring.
- The change in timing or addition of time points for any planned study assessments must be documented in a Note to File which is approved by the relevant GSK

study team member and then archived in the study sponsor and site study files, but this will not constitute a protocol amendment.

- The IRB/IEC will be informed of any safety issues that require alteration of the safety monitoring scheme or amendment of the Informed Consent Form.
- In Arm B, all procedures planned on Day 7 will be conducted on Day 9, if azacitidine is administered on 5+2 schedule: Mon-Fri (Days 1-5) and Mon-Tue (Days 8-9) schedule instead of 7 consecutive daily dosing on Days 1-7.

Whenever vital signs, 12-lead ECGs and blood draws are scheduled for the same nominal time, the assessments should occur in the following order: 12-lead ECGs, vital signs, blood draws.

If the blood draw is done first, there should be at least 15 minute interval before the vital signs and 12-lead ECGs measurements are taken

Detailed procedures for obtaining each assessment are provided in the Study Procedures Manual (SPM).

Visit Window

Baseline disease assessment should be completed within **21 days** prior to dosing start.

ECHO/MUGA should be completed within **35 days** prior to dosing start.

Pregnancy testing should be completed **7 days** prior to dosing start and all other screening assessments should be completed within **14 days** prior to dosing start.

Visits in the first 4 weeks will be allowed +/- **1 day** window.

Visits beyond the first 4 weeks will have +/- **3 days** window.

The End of Treatment visit should be completed within **14 days** from the last dose.

Time Window for PK sampling

0.5 and 1 hours post dose sampling: ± 5 minutes

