| Blood samples for exploratory studies (peripheral blood) ^{3, 11} | X | | | X | X | X | | Day 1 | X | X | |
| Bone marrow aspirate for exploratory studies ¹¹ | X | | | | | | | At time of disease assessment ¹⁷ | X ¹⁷ | X ¹⁵ | |
| Disease assessment | X | | | | | | | Day 1 | X | | |
| Bone marrow for disease assessment | X | | | | | | | as clinically indicated | X ¹⁸ | X ¹⁵ | |
| PGX samples (saliva sample) | X | | | | | | | | | | |
| PK blood sample (corresponding with exploratory BMA) ¹³ | | | | | | | | X ¹⁷ | X ¹⁷ | X ¹⁷ | |
| Transfusion Need Assessment ¹⁰ | X | | | | X | X | X | D1 | | | |
| Adverse Events | | Continuous | | | | | | | | | |
| Con Meds | | Continuous | | | | | | | | | |
| OS/PFS Assessment | | | | | | | | | | | X |

1. A blood sample will be collected for GSK2879552 PK analysis on D1 at pre-dose, 0.5, 1 hr, and 3 hrs post dose..An additional optional PK sample will be collected at 24 hours post Day 1 dose for GSK2879552 measurement.
2. A blood sample will be collected for GSK2879552 PK analysis on D7 at pre-dose, 0.5, 1 hr, and 3 hrs post dose.
3. Samples should be collected at pre-dose.
4. For women of child bearing potential only. Serum pregnancy test is required for screening, crossover and EOT visits. Urine pregnancy test is adequate during study visits.
5. A blood sample will be collected for GSK2879552 PK analysis on D15 at pre-dose and 0.5-1 hr post dose.
6. Height will be measured at screening only
7. These procedures do not need to be repeated on Day 1, if the screening visit was within 3 days and they were performed at screening.
8. PK blood sample for GSK2879552 should be taken pre-dose. PK sample will not be collected beyond 48 weeks.
9. On clinic days, study drug should be taken in the clinic after safety procedures including CBC and PK/PD samplings, if applicable are completed.
10. Platelet and blood transfusions to be assessed at designated visits and summarized per unit on a weekly cumulative basis
11. Collection of exploratory sample (peripheral blood and/or BMA) time points may be terminated at the sponsor's discretion
12. Safety laboratory blood samples (CBC, chemistry and coagulation panel) should be collected post dose on Day 7.
13. PK blood sample should be collected prior to dosing on biopsy days.
14. Azacitidine dosing can start on Day 1 of the next cycle after the cross over visit is completed.
15. Optional for all subjects

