16. Subjects are followed every 2 months to collect the survival, PFS data and the start of new treatment via chart review, or phone call contact. The follow-up will continue until death, lost to follow-up, withdrawal of consent or up to 12 months from end of treatment visit, whichever occurs first.
17. The exploratory BM sample is collected whenever the bone marrow is done for disease assessment and/or at the time of crossover, unless the sample collection is stopped per sponsor discretion; the PK blood sample will be collected pre-dose at the crossover visit if the exploratory BM sample is collected. The PK corresponding blood sample will not be collected if a regularly scheduled PK sample is already being collected during the visit.
18. A mandatory BM sample will be collected at the time of the crossover visit to establish the new baseline. A window of 14 days is allowed for this BM assessment.

Time and Events Table for Arm A – Part 2

| | SC R | Cycle 1 (28 days) | | | | | Cycle 2 and beyond | Crossover Visit | End of Treatment Visit | Post Treatment Bi-monthly Follow-Up ¹⁶ |
|----------------------------------|---------|--|----|-----|------|-----|--|--------------------|------------------------------|--|
| | | D 1 | D4 | D 7 | D 15 | D22 | | | | |
| Office Visit for Arm A (mono) | X | X | X | X | X | X | C2: D1, 7, 15 and 22 C3 and after: D1 | X | X | |
| Informed consent | X | | | | | | | | | |
| Demography | X | | | | | | | | | |
| Medical history | X | | | | | | | | | |
| Disease characteristics | X | | | | | | | | | |
| GSK2879552 Dosing ⁹ | | < ----- Daily or per dosing schedule ----- > | | | | | | | | |
| Azacitidine dosing ¹⁴ | | | | | | | | X ¹⁴ | | |
| Review subject dosing diary | | | | X | X | | Day 1 | X | X | |
| GSK2879552 Drug Dispensing | | X | | | | | Day 1 | | | |
| Complete physical exam | X | | | | | | | X | X | |
| Brief physical exam | | X ⁷ | | X | | | Day 1 | | | |
| Montreal Cognitive Assessment | X | X | | X | X | X | Day 1 | | | |
| ECOG PS | X | X ⁷ | | X | | | Day 1 | X | X | |
| Vital Signs | X | X ⁷ | | X | X | | Day 1 | X | X | |
| Height and weight ⁶ | X | X ⁷ | | X | | | Day 1 | X | X | |
| ECHO/MUGA | X | | | | | | | | | |
| 12-lead ECGs | X | X ⁷ | | X | | | Day 1 | X | X | |
| HIV, HBV and HCV Ab | X | | | | | | | | | |

| | SC R | Cycle 1 (28 days) | | | | | Cycle 2 and beyond | Crossover Visit | End of Treatment Visit | Post Treatment Bi-monthly Follow-Up ¹⁶ | |

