|---|---------|-------------------|----------------|-----------------|----------------|----------------|---|--------------------|------------------------------|--|---|
| | | D 1 | D4 | D 7 | D 15 | D22 | | | | | |
| testing | | | | | | | | | | | |
| CBC | X | X ⁷ | | X ¹² | X | X | C2: D1, 7 ¹² , 15 and 22 C3 and after: D1 | X | X | | |
| Chemistry Panel including LFT | X | X ⁷ | | X ¹² | X | X | Day 1 | X | X | | |
| Coagulation Panel including a PTT and INR | X | | | X ¹² | x | X | Day 1 | X | X | | |
| PK Blood samples | | X ¹ | X ⁸ | X ⁵ | X ² | X ⁸ | C2: D1, 7, 15 and 22 D1 of C3-C12 ⁸ | | | | |
| Pregnancy test ⁴ | X | | | | | | Day 1 | X | X | | |
| Blood samples for exploratory studies (peripheral blood) ^{3, 11} | X | | X | X | X | | Day 1 | X | X | | |
| Bone marrow aspirate for exploratory studies ¹¹ | X | | | | | | At time of disease assessment ¹⁷ | X ¹⁷ | X ¹⁵ | | |
| Disease assessment | X | | | | | | Day 1 | X | | | |
| Bone marrow for disease assessment | X | | | | | | as clinically indicated | X ¹⁸ | X ¹⁵ | | |
| PGX samples (saliva sample) | X | | | | | | | | | | |
| PK blood sample (corresponding with exploratory BMA) ¹³ | | | | | | | X ¹⁷ | X ¹⁷ | X ¹⁷ | | |
| Transfusion Need Assessment ¹⁰ | X | | | X | X | X | D1 | | | | |
| Adverse Events | | Continuous | | | | | | | | | |
| Con Meds | | Continuous | | | | | | | | | |
| OS/PFS Assessment | | | | | | | | | | | X |

1. A blood sample will be collected for PK analysis on D1 at pre-dose, 0.5hr, 1 hr and 3 hrs post dose. .
2. A blood sample will be collected for PK analysis on D15 at pre-dose and between 0.5 to 1 hour.
3. Samples should be collected at pre-dose.
4. For women of child bearing potential only. Serum pregnancy test is required for screening, crossover and EOT visits. Urine pregnancy test is adequate during study visits.
5. A blood sample will be collected for PK analysis on D7 at pre-dose, 0.5, 1 hr, and 3 hrs post dose. .
6. Height will be measured at screening only
7. These procedures do not need to be repeated on Day 1, if the screening visit was within 3 days and they were performed at screening.
8. PK blood sample for GSK2879552 should be taken pre-dose around the same time as CBC. PK sample will not be collected beyond 48 weeks.
9. On clinic days, study drug should be taken in the clinic after safety procedures including CBC and PK/PD samplings, if applicable are completed.

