Time and Events Table - Arm B (Combination with Azacitidine), Part 2

| | SC R | Cycle 1 (28 days) | | | | | Subsequent Cycles | End of Treatment Visit | Post Treatment Bi- monthly Follow-Up ¹⁶ |
|-----------------------------------|---------|--|----|------------------|------|-----|---|---------------------------|---|
| | | D 1 | D4 | D7 ¹⁸ | D 15 | D22 | | | |
| Office Visit for Arm B (combo) | X | X | X | X | X | X | C2: D1- 7 ¹⁸ , 15 and 22 C3 and after: D1-7 | X | |
| Informed consent | X | | | | | | | | |
| Demography | X | | | | | | | | |
| Medical history | X | | | | | | | | |
| Disease characteristics | X | | | | | | | | |
| GSK2879552 Dosing ⁹ | | <----- Daily or per dosing schedule -----> | | | | | | | |
| Azacitidine dosing ¹⁴ | | <--Days 1-7--> | | | | | Days 1-7 | | |
| Review subject dosing diary | | | | X | X | | Day 1 | X | |
| GSK2879552 Drug Dispensing | | X | | | | | Day 1 | | |
| Complete physical exam | X | | | | | | | X | |
| Brief physical exam | | X ⁷ | | X | | | Day 1 | | |
| Montreal Cognitive Assessment | X | X | | X | X | X | Day 1 | | |
| ECOG PS | X | X ⁷ | | X | | | Day 1 | X | |
| Vital Signs | X | X ⁷ | | X | X | | Day 1 | X | |
| Height and weight ⁶ | X | X ⁷ | | X | | | Day 1 | X | |
| ECHO/MUGA | X | | | | | | | | |
| 12-lead ECGs | X | X ⁷ | | X | | | Day 1 | X | |
| HIV, HBsAg and HCV Ab testing | X | | | | | | | | |

| | SC R | Cycle 1 (28 days) | | | | | Subsequent Cycles | End of Treatment Visit | Post Treatment Bi- monthly Follow-Up ¹⁶ |
|---|-----------------|-------------------|----------------|------------------|----------------|----------------|--|---------------------------|---|
| | | D 1 | D4 | D7 ¹⁸ | D 15 | D22 | | | |
| CBC | X | X ⁷ | | X ¹² | X | X | C2: D1, 7 ^{12, 18} , 15 and 22 C3 and after: D1 | X | |
| Chemistry Panel including LFT | X | X ⁷ | | X ¹² | X | X | Day 1 | X | |
| Coagulation Panel including a PTT and INR | X | | | X ¹² | x | X | Day 1 | X | |
| PK Blood samples | | X ¹ | X ⁸ | X ⁵ | X ² | X ⁸ | C2: D1, 7 ¹⁸ , 15 and 22 D1 of C3-C12 ⁸ | | |
| Pregnancy test⁴ | X | | | | | | Day 1 | X | |
| Blood samples for exploratory studies (peripheral blood)^{3, 11} | X | | X | X | X | | Day 1 | X | |
| Bone marrow aspirate for exploratory studies¹¹ | X | | | | | | At time of disease assessment ¹⁷ | X ¹⁵ | |
| Disease assessment | X | | | | | | Day 1 | X | |
| Bone marrow for disease assessment | X ¹⁹ | | | | | | bone marrow if clinically indicated | X ¹⁵ | |

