7.4. Evaluation of Anti-Cancer Activity

Disease assessments will be made by physical examination and laboratory evaluation, which includes a complete blood count with differential. Bone marrow aspiration should be performed if clinically indicated, and to confirm the response. Response criteria are listed in [Appendix 10](#).

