9.2. Sample Size Considerations

9.2.1. Sample Size Assumptions

Part 1: Dose Escalation

The total number of subjects to be enrolled in the dose escalation phase of Part 1 will depend on the number of subjects needed to characterize individual dose combination cohorts. The sample size is not driven by statistical considerations. However, it is anticipated that approximately 10-12 evaluable subjects will be enrolled.

Part 2: Expansion Cohorts

To determine the maximum sample size for Arm A or Arm B, Bayesian predictive adaptive design will be used for testing hypotheses:

H_0 : CBR \leq 30%

H_A : CBR \geq 50%

When maximum sample size is 28, the design will have a Type I error (α) of 0.099 and 81% power with the probability of termination is 0.90 when the treatment is futile and probability of early termination 0.183 when the treatment is effective (true RR=0.5).

In Part 2, a maximum of 28 subjects will be enrolled in Arm A and Arm B expansion cohort, respectively. If both arms enroll the maximum number of subjects, this will result in 56 subjects total randomized to Arm A and Arm B with 1:1 randomization ratio.

Enrollment into Arm A or Arm B may be halted early based on results from interim analyses incorporating emerging response data. Response data from a minimum of 10 evaluable subjects will be required per arm before it may discontinue enrollment for futility.

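### Arm A has no disease assessment scheduled at the End of Treatment visit while Arm B does, and the protocol gives no reason

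*Protocol*

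**What the plan says.** Section 7.1 has four Time and Events tables. In Arm A Part 2 the columns after Cycle 1 run "Cycle 2 and beyond | Crossover Visit | End of Treatment Visit". In Arm B Part 2 they run "Subsequent Cycles | End of Treatment Visit". Both tables print the disease-assessment row as "Disease assessment | X | | | | | | Day 1 | X". In Part 1, which has one more Cycle 1 column, both arms print "Disease assessment | X | | | | | | | Day 1 | X", again over different column orders. No footnote or text comments on the difference.

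Section 7.4 sets no arm-specific schedule: "Disease assessments will be made by physical examination and laboratory evaluation, which includes a complete blood count with differential". Bone marrow is added when clinically indicated and to confirm response. Section 7 says of the exit visit: "The End of Treatment visit should be completed within 14 days from the last dose".

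Section 4.6 allows crossover only after IWG progression without intolerable toxicity, and adds: "In each case, approval for crossover has to be granted by GSK Medical Monitor". Section 4.7 lists other reasons for stopping, including adverse events, investigator's discretion, intercurrent illness and withdrawal of consent.

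Section 9.2.1 plans "56 subjects total randomized to Arm A and Arm B with 1:1 randomization ratio". Section 9.4.1 counts unknown or missing response as non-response, censors PFS at the last adequate assessment, and plans CBR and ORR differences between arms with 95% CIs. Section 9.1.2 sets up no formal between-arm hypothesis.

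**The concern.** The Crossover Visit takes the place of an exit assessment only for Arm A subjects who progress and are approved to cross over. An Arm A subject who stops for toxicity, withdraws, or progresses without being crossed over has no scheduled disease assessment on leaving treatment. An Arm B subject with the same course has one.

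The primary endpoint makes this matter. CBR includes stable disease, which Appendix 10 ties to absence of progression for more than 8 weeks, so whether a subject counts can depend on whether a last assessment exists. A first haematologic improvement, or a progression, present at exit can likewise be recorded in one arm and not in the other. PFS censoring follows the last adequate assessment and so can differ too. The non-response rule gives the CBR effect one direction: Arm A can only lose.

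**Working it through.** **1. Is the blank cell real?** Reading the Part 2 rows against their headers:

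| Column | Arm A Part 2 | Arm B Part 2 |
|---|---|---|
| Screening | X | X |
| Cycle 1 visits | blank | blank |
| Cycle 2 onward | Day 1 | Day 1 |
| Crossover Visit | X | no such column |
| End of Treatment | **blank** | **X** |

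A column shift in the extracted text is ruled out. In the same Arm A table, the CBC and bone-marrow rows carry marks under both Crossover and End of Treatment. Part 1 gives the same result.

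**2. What is collected at Arm A End of Treatment?** A complete physical examination and CBC are scheduled, and marrow is optional, as in Arm B. The Section 7.4 inputs exist; the response assessment is not scheduled.

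**3. Which subjects can be affected?** Cycles last 28 days.
- Cycle 3 Day 1 = 2 × 28 + 1 = Day 57, which is 56/7 = 8.0 weeks after first dose.
- Cycle 4 Day 1 = 3 × 28 + 1 = Day 85, which is 84/7 = 12.0 weeks.

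If stable disease is counted from first dose, a subject who stops between these visits, without progression or earlier response, can be credited at End of Treatment in Arm B but has no scheduled assessment for it in Arm A. The 14-day visit window widens this a little, since a last dose from week 8 − 2 = 6 can lead to an exit visit after week 8. Subjects who reach Cycle 4 Day 1 are assessed there in both arms, and responders by Cycle 3 Day 1 count in both arms.

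The time origin is not stated. Baseline assessment may be up to 21 days before dosing, so counted from baseline Cycle 3 Day 1 could be as late as (56 + 21)/7 = 11.0 weeks. Visits after week 4 also have a ±3-day window, so Cycle 3 Day 1 can fall 53 to 59 days after first dose.

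**4. The plan's own operating characteristics.** Inputs: the Table 5 futility limits (stop at ≤1/10, 2/12, 3/14, 3/16, 4/18, 5/20, 6/22, 8/24, 9/26) and success at ≥12/28. The probability of each running count is carried forward subject by subject, removing paths that meet a stopping limit. This gives:
- type I error at CBR 0.30: 0.0991 (stated 0.099);
- power at CBR 0.50: 0.8174 (stated 81%).

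**5. Sensitivity to uncredited successes.** Each one is 1/28 = 3.6 percentage points. Lowering the success probability to (14 − k)/28 and rerunning the recursion:

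| k (assumed) | Success probability | Arm A power |
|---|---|---|
| 0 | 14/28 = 0.500 | 0.817 |
| 1 | 13/28 = 0.464 | 0.702 |
| 2 | 12/28 = 0.429 | 0.560 |
| 3 | 11/28 = 0.393 | 0.408 |

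The protocol gives no value for k.

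**6. Between-arm comparison.** Suppose both arms have true CBR 0.50 and a share m of Arm A successes goes uncredited (assumed). The spurious difference favouring Arm B is 0.50 × m. The exact size of a two-sided 5% chi-square test with 28 per arm is then:

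| m (assumed) | Spurious difference | Chi-square size |
|---|---|---|
| 0 | 0 | 0.045 |
| 5% | 2.5 points | 0.049 |
| 10% | 5 points | 0.060 |
| 20% | 10 points | 0.109 |

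**The case against.** The sponsor can fairly say that this is a missing mark, not missing data. Examination and CBC are taken at Arm A End of Treatment, and haematologic improvement and the count-based progression criteria in Appendix 10 can be scored from blood values. Day 1 assessments are identical in both arms. Each arm is tested separately against 30%, the chi-square test is planned only if data warrant, and a loss in Arm A cannot inflate a false claim of Arm A activity. All of that stands and limits the severity. It does not remove the inconsistency: whether the exit visit is scored in Arm A is left to site habit, while in Arm B it is required.

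Three stronger readings are tempting and are not supported.

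- **That every Arm A subject stopping in cycle 3 with stable disease is lost as a success.** Appendix 10 gives no time origin for the 8 weeks, and the visit window puts some Cycle 3 Day 1 visits past it. Loss is possible, not certain.
- **That this cell reduces Arm A power to 0.41.** Three lost successes would be 3 of an expected 14, about one in five, all falling in a narrow window. The figure shows how sensitive the rule is to lost successes; it does not estimate the effect of this cell.
- **That progression in Arm A will be dated up to two months late.** Crossover and stopping for progression already require IWG progression, so that progression has been assessed. The two-monthly follow-up allows chart review, which may recover the actual date.

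**Conclusion.** Wrong as written: the two arms have different exit schedules for the assessment behind the primary endpoint, with no explanation. Ascertainment of stable disease, late response and progression, and PFS censoring, can therefore differ between randomised arms. For CBR the direction is known, since a loss lowers Arm A; the size is not. The effect is confined mainly to subjects who stop between Day 1 assessments without an earlier response and without crossing over, notably around weeks 8 to 12 if stable disease is counted from first dose. The power and chi-square figures rest on assumed numbers of uncredited subjects and serve only to show scale. The severity is should-fix. The documents do not support saying that the separate Arm A test against 30% is invalid.

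**What to change.** Reconcile the tables. Mark disease assessment at End of Treatment in the Arm A Part 1 and Part 2 tables for subjects who do not cross over, scored by Appendix 10 from the examination and CBC already scheduled there, as in Arm B. Marrow stays optional in both arms. The cost is one cell in each of two tables and a short footnote, with no new procedure or visit. It should be done prospectively, because an assessment that was never scheduled may not be recoverable at analysis. Stating the time origin for the 8-week stable-disease requirement in Appendix 10 would settle which exit assessments can count, again at the cost of one line.

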7.2. Screening and Critical Baseline Assessments

Cardiovascular medical history/risk factors (as detailed in the CRF) will be assessed at screening.

The following demographic parameters will be captured: year of birth, sex, race and ethnicity.

Medical/medication/family history will be assessed as related to the inclusion/exclusion criteria listed in Section 5.

Procedures conducted as part of the subject's routine clinical management [e.g. blood count] and obtained prior to signing of informed consent may be utilized for Screening or baseline purposes provided the procedure meets the protocol-defined criteria and has been performed within the timeframe defined in the Time and Events Schedule.

